## INTERVENTION PROTOCOL

From the following scheme (Scheme 3), each training session of the muscle strengthening program was structured for each of the intervention groups, which was based on the principles of training and the Earl and Hoch protocol described in the theoretical framework.

*Scheme 3: A y B Strengthening Program*

After the adjustments described in the pilot test, the strengthening program was applied to the forty patients who were previously randomized to the intervention protocols for groups A and B.

Each of the exercise sessions lasted approximately 45 to 60 minutes, of which, the first 8 to 10 minutes were dedicated to the initial warm-up exercises, the same for program A and B, which gave way to the phase central to the session, that is to say the strengthening exercises: group B took about five minutes less to complete it, because they performed an exercise less than group A in each of the three phases set out in the program; This phase of strengthening lasted approximately 20 to 30 minutes of the total session.

Each session was divided into four parts, of which the second part (central strengthening phase) included between 24 and 28 exercises in total, group A and B respectively. In addition to this, the anatomical conditioning phase was carried out in two weeks, in which 5 to 6 strengthening exercises were prescribed depending on the treatment group, but for both groups the volume was two sets of 10 repetitions, with approximately 30 seconds rest between sets and between exercises, with an execution speed of 1/1 (concentric / eccentric contraction ratio) that allowed patients to adapt to adequate movement control and therefore, joint protection.

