Later, to evaluate if there were differences between the groups of treatment after the intervention on the variables of interest, deltas were generated from the Kujala test, EVA, number of squats, Q angle, balance, physical activity and core strength. with iron and trunk extension, evaluating normality by means of graphic and numerical methods. For the analysis of the differences of medians between the groups, taking into account that the outcomes did not present a normal distribution, and assuming the assumption of independence of the variables, we proceeded to use the non-parametric Mann-Whitney U test. Finally, through the Wilcoxon test, intragroup differences were evaluated for strength, pain and physical activity components.

The hypothesis tests were presented in two tails with an alpha of 0.05 and all the analyzes were executed with the statistical program STATA version 14.0.

BASELINE:

Study population

Therapeutic Effect of Two Muscle Strengthening Programs in Patients with Patellofemoral Pain Syndrome

Table 5 describes the general characteristics of the study population at baseline. There were no significant differences between the two intervention groups (A and B), which means that the randomization was adequate; however, in the total score of the Kujala test there was a difference of 12.5 points between the groups, with a lower score for group B (53.0), which indicates better core strength for these patients. Finally, the sex variable was defined as categorical and the rest of the variables as continuous, for which the medians and their respective interquartile range (IR) are reported, taking into account that the variables did not have a normal distribution.

Table 5: Baseline variables of the study population

Variables	Treatment A (n 20) Medium (RI)	Treatment B (n 20) Medium (RI)	Value p ^a
Sex * (Male, Ref)			
Female	90 (65.7-97.6) *	90.0 (65.7-97.6) *	1,000 ^b
Age	32.5 (25.5-38.0)	29.0 (25.0-36.5)	0,569
Initial weight (Kg)	64.6 (55.3-72.4)	62.7 (52.9-68.5)	0.379
Size (cm)	160 (156.5-167.0)	159.5 (154.0-163.0)	0.423
IMC	25.4 (21.5-27.9)	23.8 (22.3-25.2)	0.456
% of fat	35.4 (28.9-40.4)	35.4 (24.5-38.7)	0,714
% muscle	26.9 (24.5-28.9)	26.2 (24.6-29.0)	0.849
Visceral fat	6 (3.5-7.09)	5 (4.0-6.0)	0.433
IPAQ (minutes)	3003 (1116-4638)	1617 (944-6138)	0,588
Pain	7.5 (5.5-9.0)	7.0 (5.5-8.5)	0.764
Kujala total score	65.5 (42.5-72.5)	53.0 (44.5-71.5)	0,892
Q angle			
Straight	19.0 (15.0-20.0)	18.0 (15.0-20.0)	0,557

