To evaluate the effect of muscle strength on the alignment of the knees and analyze the effect of muscle strength on the unipodal balance, **Table 8** shows the deltas of the medians (changes or differences observed after the intervention) for each of the treatment groups and for each of the variables measured at the beginning and end of the intervention.

In this way, when they include or add exercises for the strengthening of the core, to the traditional treatment of SPF or anterior knee pain, the quality of life measured with the Kujala test in these patients increases, especially by the significant reduction of pain, highlighting for example, that for the total score of the Kujala test, there was a statistically significant difference ($p = 0.025$), with an increase of 5 points for group A (group A = 23.0, group B = 17.0), which indicates that the population of the study group improved their quality of life more after the intervention compared with the people of group B. A similar effect is observed in the increase of the strength of the core musculature for group A, especially in the oblique force evaluated with the side plate, with a difference of 30 seconds for group A, and only five seconds for group B on the left lateral plate, with a statistically significant p value (<0.001).

Therapeutic Effect of Two Muscle Strengthening Programs in Patients with Patellofemoral Pain Syndrome
On the other hand, the differences for the total pain evaluated with EVA were -6 and -4 for group B, with an interquartile range (-10; -4) and (-7; -3) respectively. Although p was not statistically significant, these differences were clinically relevant. For the hip and knee muscle strength, measured with the squat test, there was no statistically significant difference in the median of the deltas between the treatment groups, but there was one in each group, which means that all of them increased strength muscle in hips and knees, as a result of strengthening for these muscle groups.

Table 8: Effect of muscle strengthening on pain, knee alignment, core, hip and knee strength and balance by treatment groups.

Variable	Treatment A			Treatment B			Value p *
	Initial Medium (RI)	Final Medium (RI)	Delta Medium (RI)	Initial Medium (RI)	Final Medium (RI)	Delta Medium (RI)	
Pain (EVA)	7.5 (5.5-9.0)	2 (0-2)	-6 (-10; -4)	7.0 (5.5-8.5)	2.0 (0-4)	-4 (-7; -3)	0.058

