Table 10: Correlation between differences in muscle strength and balance by treatment groups

Therapeutic Effect of Two Muscle Strengthening Programs in Patients with Patellofemoral Pain Syndrome

Variable	Squats	
Balance	Treatment A *	Treatment B *
Right with open eyes	0,558	0.121
Left with open eyes	0,554	0.110
Right with closed eyes	0.390	0.009
Left with closed eyes	0.008	-0.244

* Spearman correlation coefficient.

With the previously stated results, the alternative hypothesis of this study is rejected, which means that adding core exercises to traditional hip and knee muscle strengthening for the treatment of anterior knee pain in patients diagnosed with SPF is more effective in reducing pain and improving the quality of life of these people, they do only hip and knee strengthening exercises.

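### The SAP's closing decision says the alternative is rejected yet concludes that group A is superior, and it claims a pain benefit that the between-group test does not support

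*SAP*

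**What the plan says.** The SAP's Bivariate Analysis section sets the rule. For differences between groups in the change scores, "we proceeded to use the non-parametric Mann-Whitney U test", and "The hypothesis tests were presented in two tails with an alpha of 0.05".

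The Post-Intervention Results section applies it. For the Kujala total score, which that section treats as the measure of quality of life, it reports a significant difference in favour of group A: median change 23.0 against 17.0, p = 0.025. For pain on the EVA (visual analogue) scale, the median changes are -6 and -4, Table 8 gives p = 0.058, and the text comments: "Although p was not statistically significant, these differences were clinically relevant".

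The final paragraph under Muscular Strength and Static Balance, after Table 10, then gives the overall decision. It says that "the alternative hypothesis of this study is rejected, which means that adding core exercises to traditional hip and knee muscle strengthening" and, later in the same sentence, that this addition "is more effective in reducing pain and improving the quality of life of these people" than hip and knee strengthening alone.

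**The concern.** The two halves of the closing sentence conflict. A two-sided test of no difference ends in rejecting or not rejecting the null. If the alternative really had been rejected, there would be no ground for calling group A better; if group A is better, it is the null that was rejected.

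The second problem remains once the first is mended. The sentence gives one verdict covering pain and quality of life together, although the SAP's own tests give different decisions for the two. A reader who takes the trial's result from its closing statement would carry away a between-group pain benefit that the test did not show at the stated level. In the text available, no other sentence frames the result as a decision on a hypothesis.

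**Working it through.** **Inputs**

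- Rule: two-sided, alpha 0.05, Mann-Whitney U on the change scores (SAP, Bivariate Analysis).
- Group size: 20 and 20 at baseline (SAP, Table 5), consistent with the protocol's Intervention Protocol section, where "the strengthening program was applied to the forty patients who were previously randomized to the intervention protocols for groups A and B".
- Between-group p-values and quartiles of change: SAP, Table 8.
- The hypotheses are not worded in the text available for this review. *Alternative* is therefore taken in its usual sense, a difference between groups.

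**Step 1. Apply the rule to the two outcomes the sentence names.**

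| Outcome | Median change A (quartiles) | Median change B (quartiles) | p | Decision on the null at 0.05 |
|---|---|---|---|---|
| Kujala total (quality of life) | 23.0 (16.0 to 37.0) | 17.0 (8.0 to 24.0) | 0.025 | rejected, in favour of A |
| EVA pain | -6 (-10 to -4) | -4 (-7 to -3) | 0.058 | not rejected |

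**Step 2. Try the one-word repair.** Put *null* in place of *alternative*. For Kujala the sentence becomes correct. For pain it becomes a claim that the null was rejected with p = 0.058, which fails the SAP's own alpha.

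**Step 3. Check that the two p-values were not interchanged.** This is a rough normal approximation from the printed quartiles, assuming 20 per group at the end: mean = (q1 + median + q3)/3, SD = (q3 - q1)/1.35, SE = sqrt(SD_A²/20 + SD_B²/20).

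- Kujala: means 76/3 = 25.33 and 49/3 = 16.33; SDs 21/1.35 = 15.56 and 16/1.35 = 11.85; SE = 4.37; z = 9.00/4.37 = 2.06; p about 0.04.
- EVA: means -20/3 = -6.67 and -14/3 = -4.67; SDs 6/1.35 = 4.44 and 4/1.35 = 2.96; SE = 1.19; z = -2.00/1.19 = -1.67; p about 0.09.

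This does not reproduce the Mann-Whitney test, but both values fall on the same side of 0.05 as the printed ones. Nothing suggests a swap.

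**Step 4. Context from the rest of Table 8.** It holds 14 between-group tests.

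- Five are below 0.05: Kujala 0.025, prone plank <0.001, right and left side plank <0.001 each, and trunk extension 0.001.
- Nine are not: EVA 0.058, squats 0.670, IPAQ 0.492, Q angle 0.819 and 0.672, and balance 0.916, 0.282, 0.671 and 0.349.

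No primary outcome or multiplicity rule appears in the text available. If the 14 tests were independent and every null true, the chance of at least one rejection would be 1 - 0.95^14 = 0.51. Under Holm over all 14, Kujala is the fifth smallest p, so its adjusted value is 10 × 0.025 = 0.25. Over only the two named outcomes, Holm gives 2 × 0.025 = 0.050 for Kujala, on the boundary, and 0.058 for EVA. Pain is not significant on any of these bases.

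**The case against.** **A translation slip.** The English is rough throughout; planks appear as irons, plates and a griddle. *Alternative* for *null*, or a lost *not*, is the likeliest explanation of the first fault. The results text states the direction and significance of Kujala and the non-significance of pain, and Table 8 prints every p-value. This stands. A reader might infer that the documents leave the trial's result open, so that either answer could be taken from them. They do not: only someone reading half of one sentence in isolation would be misled about direction.

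**Unworded hypotheses.** The sentence would be coherent if the study had labelled no difference as its alternative. Nothing in the text suggests this, and the pain claim would be no better supported.

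**Pain supported by other results.** Table 9 shows p < 0.001 for pain within each group, and the SAP calls the between-group difference clinically relevant. The within-group tests show that both groups changed, not that A changed more. Clinical relevance may be argued from the medians, but it is not a hypothesis decision. The SAP also sometimes treats Kujala as a measure of knee pain. However, the results section assigns quality of life to Kujala and pain to EVA, and reports no between-group test of the Kujala pain item after treatment. Using the Kujala total for both claims would count one result twice.

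**Most of Table 8 is beside the point.** A reader might set nine non-rejections out of 14 against the sentence. It claims only pain and quality of life, so the relevant tally is one of two. This objection also stands.

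**Conclusion.** The closing decision needs correction on two counts: it names the wrong hypothesis, and it claims superiority on pain with p = 0.058 against a stated alpha of 0.05. The claim on quality of life agrees with the SAP's unadjusted rule (p = 0.025). The fault lies in the written conclusion, not in any test, estimate or p-value.

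This rests on the usual meaning of *alternative* and on EVA being the pain outcome, as the results section has it.

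Two stronger readings are not supported. A reader might infer that the trial shows no pain benefit; p = 0.058 with a median change two points larger in group A is a failure to reject, not evidence of equality. A reader might also infer from the adjusted value of 0.25 that the Kujala claim must go. That figure depends on treating all 14 tests as one family, and the documents neither define a family nor name a primary outcome. The supportable request is that the Kujala decision be labelled unadjusted.

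**What to change.** Replace the closing sentence with: *The null hypothesis of no between-group difference in change is rejected at 0.05 (two-sided, unadjusted for 14 tests) for Kujala total score; it is not rejected for EVA pain.* Delete the statement that core exercises give greater pain reduction.

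If other outcomes are listed, say that the null is also rejected for the prone plank, both side planks and trunk extension, and is not rejected for squats, IPAQ, Q angle and balance, all unadjusted.

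The cost is one sentence of wording and a less sweeping conclusion. No new data or analysis is needed.

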In **Table 9**, differences in medians and interquartile ranges their entire study population at the beginning and end of treatment for muscle strength, pain and level of physical activity is. It can be seen that the gluteal and quadriceps muscle strength measured with the squat test at the end of the treatment was the same in both groups, with a statistically significant p value (<0.001), which means that the whole population increased strength in a significant way.

In the same way, a similar effect was observed in the median pain measured with the VAS at the end of the treatment, because they all reported a decrease in pain, this difference being statistically significant, with a p-value less than 0.001. However, in the measurement of physical activity level with the long IPAQ at the end of the treatment, it was observed that the study population in group B spent less time practicing physical activity at the beginning of treatment, but both groups increased in time similar this practice at the end of the treatment; however, this difference was not statistically significant.

Table 9: Difference of intragroup medians for muscle strength, pain and physical activity level.

Variable	Treatment A			Treatment B		
	Initial Medium (RI)	Final Medium (RI)	Value p *	Initial Medium (RI)	Final Medium (RI)	Value p *
Squats	10.0 (8.0-18.5)	35.0 (30.0-38.0)	<0.001	12.5 (8.5-20.0)	35.0 (29.0-38.0)	<0.001
IPAQ (minutes)	3003 (1116-4638)	4275 (2587-6522)	0.029	1617 (944-6138)	4598 (2888-7344)	0.012
Pain (EVA)	7.5 (5.5-9.0)	2.0 (0.0-2.0)	<0.001	7.0 (5.5-8.5)	2.0 (0-4)	<0.001

* Wilcoxon nonparametric test

Muscular Strength and Static Balance

In **Table 10**, the correlation between the muscle and gluteus muscle strength differences measured with the squat and unipodal balance test evaluated with the One Leg Stance test with open and closed eyes by treatment groups is shown, with which it is emphasized that, for both treatment groups, the unipodal balance improved clinically significant. However, for the study group (A), this correlation was greater (strong), especially in the variable with open eyes for both lower limbs, indicating that by increasing muscle strength (glutes and quadriceps in this case) it is improved the unipodal balance. Although there is an increase in the balance for both treatment groups, there is a stronger correlation when core exercises are included, which is what happens in group A.

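### The closing conclusion claims greater pain reduction with core exercises, but the SAP's between-group test on EVA pain gave p = 0.058 against a two-sided alpha of 0.05

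*SAP*

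**What the plan says.** **Decision rule (SAP, Bivariate Analysis).** Changes from baseline were formed for several outcomes, EVA pain and Kujala among them. To compare the groups, "we proceeded to use the non-parametric Mann-Whitney U test". On error rate and sidedness: "The hypothesis tests were presented in two tails with an alpha of 0.05".

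**Between-group result (SAP, Post-Intervention Results, Table 8).** The median EVA change is -6 (IQR -10; -4) in A and -4 (-7; -3) in B, p = 0.058. The table footnote confirms that this is the Mann-Whitney test on changes between groups. The text comments: "Although p was not statistically significant, these differences were clinically relevant".

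**Within-group result (SAP, Intragroup differences, Table 9).** EVA pain has p < 0.001 in each arm by the Wilcoxon test: "because they all reported a decrease in pain, this difference being statistically significant, with a p-value less than 0.001".

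**Conclusion (SAP, closing paragraph after Table 10).** The paragraph opens with "the alternative hypothesis of this study is rejected, which means that adding core exercises to traditional hip and knee muscle strengthening" and continues, for patients with anterior knee pain, "is more effective in reducing pain and improving the quality of life of these people". The comparison is with hip and knee exercises alone. Nothing qualifies the pain claim.

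**The concern.** Pain is the first benefit named in the conclusion of a trial in anterior knee pain. Someone who reads only that sentence takes away a between-group pain benefit that the SAP's own test and alpha did not give, and that the results text had already called non-significant.

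Two other features make the misreading more likely.

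- Post-Intervention Results says, of adding core work to usual treatment, that "the quality of life measured with the Kujala test in these patients increases, especially by the significant reduction of pain". The pain reduction is significant within each arm, but in that sentence it reads as a comparison of A with B.
- The closing sentence rejects the alternative hypothesis and then asserts what the alternative would state. This is probably a slip for the null hypothesis, but changing the one word would still leave the sentence wrong for EVA pain.

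**Working it through.** **Inputs**

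- Alpha 0.05, two-sided; Mann-Whitney on changes (Bivariate Analysis).
- EVA changes -6 (-10; -4) and -4 (-7; -3), p = 0.058; Kujala total changes 23.0 and 17.0, p = 0.025 (Table 8).
- 20 per arm at baseline (Table 5). Table 8 gives no n for the changes, so 20 is an assumption there, and 17 is used as an illustrative lower value.

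The Mann-Whitney p-value cannot be reproduced without patient-level data. What can be checked is the decision and roughly what it implies.

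**1. Decision**

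For two-sided p = 0.058, |z| = 1.896, below the critical value 1.960. The null is not rejected for EVA pain. For Kujala, p = 0.025 gives |z| = 2.241, which exceeds 1.960.

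**2. Effect implied by the p-value**

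The Mann-Whitney effect is θ = P(A better) + ½P(tie). With n per arm, ties ignored and the null standard error, SE = √[(2n+1)/(12n²)], and θ = 0.5 + z × SE.

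| Outcome | n per arm | SE | θ | Approx. 95% CI |
|---|---|---|---|---|
| EVA pain | 20 | √(41/4800) = 0.0924 | 0.5 + 1.896 × 0.0924 = 0.675 | 0.494 to 0.856 |
| EVA pain | 17 | √(35/3468) = 0.1005 | 0.5 + 1.896 × 0.1005 = 0.690 | 0.494 to 0.887 |
| Kujala total | 20 | 0.0924 | 0.5 + 2.241 × 0.0924 = 0.707 | 0.526 to 0.888 |

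The EVA intervals include 0.5; the Kujala interval does not.

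**3. On the EVA scale**

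- Take the shift to be the gap in median changes, -6 - (-4) = -2 (assumption). The SE that matches p = 0.058 is 2/1.896 = 1.055, so the interval is -2 ± 1.96 × 1.055 = -4.07 to +0.07.
- Alternatively, use a normal approximation with SD = IQR/1.349: 6/1.349 = 4.45 in A and 4/1.349 = 2.97 in B. With n = 20, SE = √(4.45²/20 + 2.97²/20) = 1.195, and the t interval is -4.43 to +0.43. With n = 19 it is -4.5 to +0.5.

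Both approaches include zero, and both include differences of 4 points in favour of A.

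**4. What else could support the pain claim**

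- Table 9 tests change within each arm. Both arms improved, and both final EVA medians are 2. These tests say nothing about A against B.
- The squat outcome has the same structure: p < 0.001 within each arm and 0.670 between arms. There the text reports no between-group difference. Pain is handled inconsistently with that.

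**5. Related figures**

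- Table 8 has 14 between-group tests. Five are below an unadjusted 0.05: Kujala total and the four core-endurance measures.
- The text describes the Kujala difference as "with an increase of 5 points for group A (group A = 23.0, group B = 17.0", but 23.0 - 17.0 = 6.0.
- Holm adjustment over the 14 tests, with each p < 0.001 set to 0.001, gives 14 × 0.001 = 0.014 for the core measures and 10 × 0.025 = 0.25 for Kujala.

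**The case against.** **Kujala as a pain measure.** This is the best defence. The SAP describes the baseline Kujala comparison as assessing pain, and the captions to Graphs 1, 3 and 4 label Kujala data as anterior knee pain. On that reading the pain claim could rest on p = 0.025. It does not hold up for the conclusion. Tables 5 and 8 list pain and Kujala as separate rows, Post-Intervention Results uses Kujala as the quality-of-life measure, and the closing sentence names pain and quality of life as two benefits. No post-treatment comparison of a Kujala pain item between arms is reported.

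**A near miss in the right direction.** True: the medians favour A, and the p-value is close to alpha. A one-sided p would be 0.029, but the SAP specifies two tails. Closeness supports saying not demonstrated rather than no effect; it does not support an unqualified superiority claim.

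**Clinical relevance.** The supplied text gives neither a relevance threshold nor an interval for the difference, so this remark cannot carry the claim.

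**Openness and pre-specification.** The non-significant p-value is printed, so nothing is hidden; the error lies in the conclusion. The SAP is also written in the past tense, and it justifies the test by the observed non-normality, so one cannot say that the test was fixed in advance. It is nevertheless the only between-group test the SAP states for EVA.

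**The approximations.** The θ values count ties as half, and ties are likely on EVA, so the strict probability of a better result is lower. The first EVA-scale interval is back-solved from p and adds no independent evidence. The n is also uncertain. If EVA runs 0 to 10 (assumption) and all 20 A patients contribute, a lower-quartile change of -10 under averaging or interpolating definitions needs six patients with baseline 10. The baseline upper quartile would then be 10, not the printed 9.0. These points stand, but the decision needs only 0.058 > 0.05.

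**Conclusion.** The concern holds. By the SAP's stated test, sidedness and alpha, superiority of group A on EVA pain is not demonstrated, and the closing sentence contradicts both Table 8 and the results text. The decision depends only on printed figures.

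The size of the uncertainty rests on approximations from summary data: θ of about 0.68 to 0.69 with a lower limit just under 0.5, and a shift interval from just over 4 points in favour of A to slightly beyond zero. These assume 17 to 20 patients per arm, no tie correction and, for the shift, either the gap in medians or normality. They show that a worthwhile benefit and no benefit are both compatible with the data.

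The quality-of-life half is nominally supported by Kujala at unadjusted 0.05. The statement that the alternative hypothesis is rejected is wrong beside an assertion of superiority. This must be fixed, because it changes what the trial says it found about pain.

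**What to change.** 1. Replace the closing sentence with a decision for each outcome, for example:

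> At an unadjusted two-sided 0.05, the null hypothesis of no difference between programs was rejected for the Kujala total (p = 0.025) and the four core-endurance measures (p ≤ 0.001). It was not rejected for EVA pain (p = 0.058). Median changes in pain (-6 and -4) favoured group A, but superiority on pain was not demonstrated, and absence of an effect was not shown.

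2. Remove the statement that the alternative hypothesis is rejected.
3. In Post-Intervention Results, label the significant pain reduction as a within-arm finding and refer to Table 9.
4. Report the Hodges-Lehmann between-group difference in EVA change with its 95% CI and the number analysed in each arm, and check the printed quartiles. Keep the clinical-relevance remark only beside that interval and with the threshold used. If no threshold was on record beforehand, say that it was chosen after the results.
5. Reconcile the 5-point Kujala difference in the text with the 6.0 given by the printed medians.
6. Optional: show Holm-adjusted p-values over the 14 tests as a labelled post hoc sensitivity analysis, since the supplied text names no primary outcome. Kujala would then be 0.25, which is a reason to keep the word unadjusted in item 1.

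The cost is rewording, one estimate from existing data, and confirmation of the n analysed and any threshold. No new data are needed. The price is a less favourable headline on pain.
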